### **11.3.3 Safety Laboratory Tests**

Routine safety laboratory tests (CBC/Diff and serum chemistry) will be performed at Screening, Week 4, and Week 8. Any out-of-range laboratory result that is considered clinically significant by the investigator will be recorded as an AE and should be confirmed by repeat testing at the discretion of the investigator. Clinically significant laboratory abnormalities at any visit will be followed to resolution (return to normal or to the baseline state) or until clinically stable as determined by the investigator.

### **11.3.4 Pregnancy Tests**

All female subjects of childbearing potential will undergo serum pregnancy testing at Screening, Week 4, and Week 8. In addition, urine pregnancy testing will be performed at Screening and prior to randomization at Baseline, and at Week 12 (4-week post-treatment follow-up visit).

## **11.4 Other Evaluations**

### **11.4.1 Dermatology Life Quality Index (DLQI)**

The DLQI questionnaire will be administered to subjects at Day 0 (Baseline), Week 4, Week 8/End of Treatment and Week 12 (4-week post-treatment follow-up visit).

### **11.4.2 Photography**

Photographs will be taken of target lesion and one other psoriasis lesion at all study visits starting with baseline. Only subjects who provide written photographic consent will be included in photography. Reference the photography manual for this study.

## **11.5 Adverse Events**

### **11.5.1 Definition of Adverse Event**

An AE is any untoward medical occurrence in a patient or clinical investigation subject administered a medicinal product and which does not necessarily have a causal relationship with the study drug. AEs include any unfavorable and unintended illness, sign, symptom, clinically significant laboratory test abnormality, or disease temporally associated with the use of a medicinal product that has appeared or worsened during the course of the clinical trial, regardless of causal relationship to the study drug(s) under study. The collection of nonserious AEs and serious adverse events (SAEs) should begin following the subject's completion of the consent process to participate in the study.

### 11.5.2 Documenting Adverse Experiences

It is the responsibility of the investigator to document all AEs that occur during the course of the study. The AEs should be documented as a single medical diagnosis. When this is not possible, the AE should be documented in terms of signs and/or symptoms observed by the investigator or reported by the subject at each study visit.

All AEs occurring after the subject signs the informed consent through the last study visit must be reported, regardless of whether or not the AEs are considered drug-related. All AEs, whether in response to a query, observed by the study site personnel, or reported spontaneously by the subject, will be recorded.

At each visit during the study, the subject will be assessed for the occurrence of new and ongoing AEs. Cutaneous tolerability signs and symptoms that result in the subject's requiring a concomitant therapy or discontinuation from the study will be reported as an AE. The following data will be collected on all AEs and recorded on the appropriate eCRF:

- Event name (diagnosis preferred, if unknown, record the signs/symptoms)
- Onset date and end date
- Maximum intensity (severity)
- Seriousness
- Action taken regarding study drug
- Corrective treatment, if given
- Outcome

In addition, the investigator's assessment of causality will be recorded.

Vital sign abnormalities are to be recorded as AEs only if they are clinically significant (for example: are symptomatic, requiring corrective treatment, leading to discontinuation or fulfilling a seriousness criterion).

### 11.5.3 Serious Adverse Events

All AEs will be assessed as either serious or nonserious.

An SAE or serious adverse reaction is defined as any untoward medical occurrence that at any dose:

- Results in death
- Is immediately life threatening, (the term "life threatening" in the definition of "serious" refers to an event in which the subject is at risk of death at the time of the event; it does not refer to an event which hypothetically might have caused death if it were more severe)
- Requires in patient hospitalization or prolongation of existing hospitalization (hospitalization for elective surgery for a baseline condition is not considered an AE)
- Results in persistent or significant disability/incapacity (permanent or substantial disruption of a person's ability to conduct normal life functions)
- Is a congenital anomaly/birth defect
- Is a medically important event that may not be immediately life threatening or result in death or hospitalization, but may jeopardize the subject and may require medical or surgical intervention to prevent 1 of the above listed outcomes

Note: A spontaneous abortion will be considered an SAE, and must be reported to the sponsor/designee within 24 hours of your awareness of the event.

### 11.5.4 Assessment of Severity

The severity assigned to an AE should be determined by the maximum severity of the AE. The categories described below should be used to estimate the severity of AEs:

- Mild: Transient or mild discomfort; no limitation in activity; no medical intervention/therapy required
- Moderate: Mild to moderate limitation in activity; some assistance may be needed; no or minimal medical intervention/therapy required
- Severe: Marked limitation in activity; some assistance usually required; medical intervention/therapy required; hospitalization or prolongation of current hospitalization possible; may be incapacitating or life threatening

### 11.5.5 Assessment of Causality

The investigator should assess the relationship of the AE, if any, to the study drug as either “Related” or “Not Related”. The following should be taken into account when assessing SAE causality:

- Positive temporal relationship to study drug, such as if the study drug was withdrawn and the SAE resolved or the event recurred after re introduction.
- If there is a reasonable possibility that the AE is associated with an underlying or concomitant illness.
- Possible association with previous or concomitant therapy.
- No temporal relationship to the study drug and/or a more likely alternative etiology exists.
- If the AE is directly related to study procedures or there is a lack of efficacy.

### 11.5.6 Reporting of Serious Adverse Events

Adverse events classified as “serious” require expeditious handling and reporting to sponsor or designee within 24 hours of investigational center notification to comply with regulatory requirements.

All SAEs, whether related or unrelated to study drug, must be immediately reported to the medical monitor within 24 hours of the investigator’s awareness of the event. All SAEs must be reported via confirmed facsimile transmission and must be submitted on a written SAE report form signed by the investigator within 24 hours of the investigator’s awareness of the event.

The fax number for reporting an SAE is:

Investigators should not wait to receive additional information to fully document the event before notifying Medical Monitor of an SAE. If only limited information is initially available, follow-up reports are required. Additional relevant information such as hospital records and autopsy reports should be provided to Sponsor/designee as soon as they are available. Should the investigator become aware of an SAE (regardless of its relationship to investigational product) that occurs within 30 days after stopping the study drug, the SAE must be reported in accordance with procedures specified in this protocol.

The investigator should take all appropriate measures to ensure the safety of the subjects, notably he/she should follow a subject with an SAE until the event has resolved or the condition has stabilized. This may imply that follow-up will continue after the subject has left the study, and that additional investigations may be requested by the sponsor.

#### **11.5.7 Expedited Serious Adverse Event Reports**

An AE, whether serious or nonserious, is designated unexpected (unlabeled) if it is not reported in the clinical safety section of the Investigator Brochure or if the event is of greater frequency, specificity or severity.

Expedited SAE reports are those that are both unexpected based on the reference document (Investigator Brochure or Package Insert) and are related (i.e., the relationship cannot be ruled out) to the study drug. These expedited reports are subject to reporting timelines of 7 and/or 15 calendar days to the regulatory reporting agency(ies). Valeant Pharmaceuticals will notify regulatory authorities of these AEs and all participating investigational centers in writing for submission by the investigator to the IRB/IEC. This notification will be in the form of a Safety Update to the Investigator Brochure (i.e., “15-day letter”).

Upon receiving such notices, the investigator must review and retain the notice with the Investigator Brochure and immediately submit a copy of this information to the responsible IRB/IEC according to local regulations. The investigator and IRB/IEC will determine if the informed consent requires revision. The investigator should also comply with the IRB/IEC procedures for reporting any other safety information.

#### **11.5.8 Laboratory Test Abnormalities**

If an AE should require laboratory testing in addition to that required by protocol, the results of the test(s) must be obtained by the investigational center and filed with the subject’s source documentation. Any laboratory test result that meets the criteria for an SAE must also be reported to the sponsor/designee via written SAE report form signed by the investigator within 24 hours of investigational center notification.

#### **11.5.9 Pregnancy**

All female subjects of childbearing potential must use an effective method of birth control during the course of the study, in a manner such that risk of contraceptive failure is minimized. Abstinence is allowed as a birth control method.

Before enrolling a female subject of childbearing potential in this clinical trial, the investigator must review the following information about study participation:

- Informed consent requirements
- Contraceptives in current use

Following review of this information and appropriate subject counseling, the investigator or designee and the subject must sign the informed consent before study enrollment.

During the study, all female subjects of childbearing potential should be instructed to contact the investigator immediately if they suspect they might be pregnant (e.g., missed or late menstrual period).

If a subject or investigator suspects that the subject may be pregnant prior to study enrollment, the study drug must be withheld until the results of laboratory pregnancy testing are available. If pregnancy is confirmed, the subject must not receive study drug and must not be enrolled in the study. If pregnancy is suspected while the subject is receiving study treatment, the study drug must immediately be withheld until the result of pregnancy testing is known. If pregnancy is confirmed, the study drug will be permanently discontinued and the subject will be followed until the pregnancy comes to term. A Pregnancy Report form will be submitted to the sponsor, initially and at the end of the pregnancy, which includes the outcome of the pregnancy and any complications occurring during the pregnancy or the delivery.

All confirmed pregnancies must be immediately reported to the medical monitor within 24 hours of the investigator's awareness of the pregnancy. All confirmed pregnancies must be reported via confirmed facsimile transmission and must be submitted on a written Pregnancy Report form within 24 hours of the investigator's awareness of the pregnancy.

## 12 Statistics

All statistical processing will be performed using SAS® unless otherwise stated. No interim analyses are planned. Except where noted, all statistical tests will be two-sided and will be performed at the 0.05 level of significance.

Descriptive statistics will be used to provide an overview of the efficacy and safety results. For categorical parameters, the number and percentage of subjects in each category will be presented. For continuous parameters, descriptive statistics will include n (number of subjects), mean, standard deviation, median, minimum, and maximum. Appropriate inferential statistics will be used for the primary and secondary efficacy variables.

The primary method of handling missing efficacy data will be the method of Markov Chain Monte Carlo (MCMC) multiple imputation. As a sensitivity analysis, the last observation carried forward method (LOCF) will be used (i.e., the last available on-therapy observation for a subject will be used to estimate subsequent missing data points). No imputations will be made for missing safety data.

A statistical analysis plan (SAP), describing all statistical analyses will be provided as a separate document. The SAP will be finalized prior to unblinding of the study treatments.

Amendment 1, Clinical Study Protocol, 14 October 2015

CONFIDENTIAL

## **12.1 Assessment of Efficacy**

The primary efficacy endpoint will be the percent of subjects with treatment success, defined as at least a 2-grade improvement from Baseline in IGA score and an IGA score equating to “Clear” or “Almost Clear”.

### **12.1.1 Primary Efficacy**

The primary efficacy endpoint will be used to compare once daily application of IDP-122 Lotion and vehicle.

The percent of subjects with treatment success at Week 8 will be analyzed using Cochran-Mantel-Haenszel (CMH) tests stratified by analysis center.

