**Sample size calculations:**

One hundred forty (140) IDP-122 treated subjects and seventy (70) vehicle treated subjects will have greater than 95% power to detect a statistically significant outcome for a two-sided test with an alpha level of 0.05. This is based on treatment success rates of 33.3% and 9.7% which were observed in V01-118A-201. Success was defined as at least a 2-grade improvement from Baseline in the IGA score and an IGA score equating to "Clear" or "Almost Clear".

This study will be performed in compliance with GCP including the archiving of essential study documents. This protocol follows guidelines outlined by the International Conference on Harmonization (ICH). All data furnished to the investigator and his/her staff, and all data obtained through this study, will be regarded as confidential and proprietary in nature and will not be disclosed to any third party, except for the United States Food and Drug Administration or other regulatory body, without written consent from the sponsor.

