## 7 Investigational plan

### 7.1 Overall Study Design and Plan: Description

This is a multicenter, double-blind, randomized, parallel-group study designed to assess the safety and efficacy of IDP-122 Lotion in comparison with its vehicle. To be eligible for the study, subjects must be at least 18 years of age and have a clinical diagnosis of moderate to severe psoriasis (defined as an IGA score of 3 or 4).

Approximately 210 subjects who meet the study entry criteria will be randomized in a 2:1 ratio to receive IDP-122 (HP 0.01%) Lotion and IDP-122 Vehicle Lotion, respectively. The assigned study drug will be applied topically to the affected area (as determined by the investigator at Baseline) once daily for 8 weeks. The initial application will be made at the investigational center during the day as per instruction from the study coordinator or designee. The subjects will be instructed to avoid exposure to direct sunlight, artificial ultraviolet light sources and to use protective clothing to prevent sunburn. Subjects will apply their daily treatments at home as explained by the study coordinator or designee at each investigational center. The study coordinator or designee at each investigational center will dispense 2 new containers of study drug to each subject at Baseline and Weeks 2, 4, and 6. During post-baseline study visits (Weeks 2, 4, 6, and 8) the subjects will be asked to return their used containers of study drug. Subjects will be asked to not apply study drug on day of clinic visit so that subject can apply during the visit after assessments are completed. Upon completion of the 8-week treatment period, all subjects will be asked to return to the investigational center 4 weeks later for a post-treatment cessation follow-up visit (Week 12). During the study, each subject will only be permitted to use Investigator approved non-medicated cleansers, moisturizers and sunscreens; no other skin care products will be permitted on the treatment areas.

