### **12.1.7 Subgroup Analyses**

Subgroup analyses will be conducted for the ITT population for the following subgroups: Baseline IGA, sex, age, ethnicity, and race. Age will be dichotomized to less than the median age of subjects and greater than or equal to the median age of subjects. Subgroup analyses will be conducted on the primary efficacy endpoint and will contain only descriptive statistics.

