### 12.8.2 Sample Size Determination

The following power calculations were computed using the observed Week 8 dichotomized IGA efficacy data in the ITT population from the Phase 2 study V01-118A-201. SAS PROC POWER with the Fisher's exact test option was used to calculate the power for various sample sizes using a two-sided test with an alpha of 0.05. Table 5 presents the efficacy estimates derived from study V01-118A-201.

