**Table 5. Percent Dichotomized IGA Success for Treatment Groups**

	IDP-122* (IDP-118 Monad (HP 0.01%) Lotion)	IDP-122 (IDP-118) ** Vehicle
Percent Success	33.3%	9.7%

Success was defined as at least a 2-grade improvement from Baseline in the IGA score and an IGA score equating to "Clear" or "Almost Clear".

\*IDP-122 refers to the (IDP-118 Monad (HP 0.01%) Lotion) used in the V01-118A-201 Study

\*\*IDP 118 Vehicle composition used in the V01-118A-201 is equivalent to the vehicle that will be used in this study (IDP 122 Vehicle Lotion).

One hundred forty (140) IDP-122 treated subjects and seventy (70) vehicle treated subjects will have greater than 95% power to detect a statistically significant outcome for a two-sided test with an alpha level of 0.05.

It was noted that the estimates extracted from the above studies are based on the LOCF method of handling missing values while the proposed Phase 3 analysis will account for missing values using multiple imputations. The power stated above sufficiently exceeds 95% which will compensate for the difference in handling of missing data.

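### The primary and gated CMH tests are valid but leave baseline IGA unused; a prespecified additive risk-difference model with analysis center and baseline IGA would add a little precision

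*Combined protocol and SAP*

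**What the plan says.** - **Endpoint.** Section 12.1 defines success as "at least a 2-grade improvement from Baseline in IGA score and an IGA score equating to" Clear or Almost Clear, which are scores 1 and 0 in Table 2. Inclusion criterion 4 (Section 8.1) admits only baseline IGA 3 or 4.
- **Primary test.** Section 12.1.1: "The percent of subjects with treatment success at Week 8 will be analyzed using Cochran-Mantel-Haenszel (CMH) tests stratified by analysis center".
- **Gated tests.** Section 12.1.2 uses the same center-stratified CMH for success at Weeks 12, 6, 4 and 2, in that order, and stops at the first non-significant result.
- **Sensitivity model.** The repeated measures model in Section 12.1.6.2 has treatment, analysis center and visit as factors, without baseline IGA.
- **Where baseline IGA does appear.** Section 12.1.7 lists it among the subgroups ("Baseline IGA, sex, age, ethnicity, and race"), which are descriptive only.
- **Randomization.** Subjects are "randomized in a 2:1 ratio to receive IDP-122 (HP 0.01%) Lotion and IDP-122 Vehicle Lotion, respectively" (Section 7.1). Section 9.2 keeps the ratio within each center and describes no stratification by severity.
- **Power.** Section 12.8.2: "SAS PROC POWER with the Fisher's exact test option was used to calculate the power". The synopsis adds: "This is based on treatment success rates of 33.3% and 9.7% which were observed in V01-118A-201".

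Section 12 announces a separate SAP, to be finalized before unblinding. Its text is not among the documents reviewed, so an adjusted analysis there can be neither confirmed nor ruled out.

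**The concern.** The endpoint's own definition makes the hurdle depend on the starting grade. From grade 3, reaching IGA 1 is a 2-grade change; from grade 4 it is a 3-grade change. Given the entry criterion, the 2-grade clause adds nothing, because anyone who reaches IGA 0 or 1 has already met it.

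A variable recorded for every subject and likely to predict the outcome is normally a candidate for adjustment. Adjustment takes explained variation out of the comparison and deals in advance with a chance imbalance in severity. As the protocol stands, no inferential analysis could address such an imbalance without a post hoc choice.

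The place where this could count is the gated sequence. The documents give no expected rates or power for Weeks 12, 6, 4 and 2, and one non-significant result ends the sequence.

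**Working it through.** **1. The plan's own figure.** Inputs from Section 12.8.2, Table 5 and the synopsis: 140 v 70 subjects, 33.3% v 9.7%, two-sided alpha 0.05.

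- Pooled rate = (140 × 0.333 + 70 × 0.097)/210 = 0.2543.
- SE under the null = sqrt[0.2543 × 0.7457 × (1/140 + 1/70)] = 0.0637.
- SE under the alternative = sqrt[0.333 × 0.667/140 + 0.097 × 0.903/70] = 0.0533.
- Power = Φ[(0.236 − 1.96 × 0.0637)/0.0533] = Φ(2.08) = 98.1%.

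Exact enumeration of Fisher's test gives 97.97%. The stated figure, greater than 95%, is reproduced. Little is left to gain at these rates.

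**2. Best possible precision gain at the planned rates.** Let f be the grade 4 share and r the grade 4 success rate divided by the grade 3 rate, the same in both arms. Both are assumptions. Holding the overall rates fixed, the grade 3 rate is the overall rate × k and the grade 4 rate is the overall rate × k × r, with k = 1/(1 − f + f × r). The adjusted variance is the within-grade binomial variance plus f(1 − f)(d3 − d4)²/210, where d3 and d4 are the risk differences by grade.

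Example, f = 0.20 and r = 0.25:

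- k = 1/0.85 = 1.176; grade 3 rates 0.392 v 0.114; grade 4 rates 0.098 v 0.029.
- Unadjusted variance = 0.002838.
- Adjusted variance = 0.002722 + 0.000033 = 0.002755.
- Reduction: 2.9% in variance, 1.5% in SE.

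| Grade 4 share | SE reduction, r = 0.75 | r = 0.50 | r = 0.25 |
|---|---|---|---|
| 10% | 0.1% | 0.3% | 0.7% |
| 20% | 0.1% | 0.6% | 1.5% |
| 30% | 0.2% | 0.9% | 2.3% |
| 50% | 0.2% | 1.3% | 4.3% |

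**3. Chance imbalance.** The SD of the between-arm difference in grade 4 share is sqrt[f(1 − f)(1/140 + 1/70)]. It is 5.2 points at f = 0.15 and 7.0 points at f = 0.35.

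**4. Additive linear model against the planned CMH.** Simulation with 14 centers of 10:5 (210/15 = 14) and 2,500 trials per setting:

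- 25% v 9.7%, baseline IGA prognostic: −0.1 to +1.5 points of power.
- 25% v 9.7%, baseline IGA not prognostic: −0.2 points.
- 10% v 3% and 12% v 3%: +0.1 to +0.5 points.
- Type I error: 3.9%-5.4%.

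Some other runs, of 4,000 to 8,000 trials, put the total difference from the CMH as high as 2.4 points, but not all of that is due to IGA. In a run of 20,000 trials, a linear model with site and no IGA already exceeded the CMH by 0.4-0.7 points. Baseline IGA itself then added 0.4 (15% grade 4, odds ratio 0.4), 0.9 (25%, 0.25) and 1.5 points (35%, 0.2).

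**5. Crossing center with IGA in the CMH.** With 15 subjects per center and 15% at grade 4, a center expects 15 × 0.15 = 2.25 grade 4 subjects, of whom 5 × 0.15 = 0.75 are on vehicle. A grade 4 stratum contains both arms with probability (1 − 0.85^5)(1 − 0.85^10) = 0.556 × 0.803 = 0.447. About 11 of the 210 subjects fall in strata that contribute nothing. Over f = 10%-50% and r = 0.25-1, power changes by −0.8 to +0.2 points at the planned rates and by −3.2 to +0.6 points at 25% v 9.7%.

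**6. Logistic Wald test with fixed center effects and IGA.** At 25% v 9.7% it does no worse than the linear model (for example 80.4% v 79.8%, CMH 78.5%; 25% grade 4, odds ratio 0.25). At low rates it fails:

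| Rates | CMH power | Logistic Wald power |
|---|---|---|
| 10% v 3% | 44.8% | 27.3% |
| 12% v 3% | 61.8% | 45.9% |

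With a 3% vehicle rate, all 70 vehicle subjects fail with probability 0.97^70 = 12%, and the treatment log odds ratio is then not estimable. Such rates are assumed, but they could arise at an early gated visit.

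**The case against.** The strongest reply is that nothing is broken. The center-stratified CMH is valid under randomization (simulated type I error 4.5%-4.9%). That error rate already covers chance imbalance in severity, baseline IGA is examined descriptively, and the primary test has about 98% power at the only rates the documents give. All of this stands.

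The reply also says that the gain rests on figures absent from the documents: the grade 4 share, success by baseline grade, and rates at the gated visits. This stands too. Lower power at the gated visits is plausible but undocumented.

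Finally, adjustment can do harm. Crossed strata usually lose power here, and a logistic Wald test can lose a great deal of it. Section 12.1.4 itself allows for a site-level logistic model, there with an interaction, proving infeasible where enrollment is low. These objections rule out those two methods. They do not touch the additive linear model on pooled analysis centers, which showed no material loss in any setting tried.

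A reader might infer that the plan gives away precision at no cost. The documents do not support that. The loss is near nil at the planned rates, and the remedy has a price: a model-based analysis and, if it replaces the CMH, a protocol amendment.

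**Conclusion.** The point holds as a minor improvement. Baseline IGA is likely prognostic by construction of the endpoint, and no inferential analysis in the protocol uses it. Using it through an additive linear model is worth almost nothing at 33.3% v 9.7%. It is worth about 0 to 1.5 points of power at 25% v 9.7%, assuming 15%-35% of subjects start at grade 4 with odds of success 0.4 to 0.2 times those at grade 3. If baseline IGA turned out not to matter, the cost was about 0.2 points.

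It would be wrong to conclude that the primary test is invalid, biased or underpowered. It would also be wrong to conclude that any form of adjustment improves on the CMH; two obvious forms can make it worse.

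**What to change.** Prespecify, for the primary and the four gated endpoints, a linear (risk-difference) regression of treatment success on treatment, analysis center as pooled under Section 12.1.4, and baseline IGA (3 v 4), with the standard error to be used named in advance. The treatment coefficient and its standard error can be combined in PROC MIANALYZE directly, without the Wilson-Hilferty step of Section 12.1.5.

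- **Beside the CMH:** SAP text only, before unblinding. State that it is supportive and does not alter the gating.
- **In place of the CMH:** a protocol amendment before unblinding, because Sections 12.1.1 and 12.1.2 name the CMH as the test.

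In either case, keep center and IGA uncrossed in the CMH, and avoid a logistic Wald test with fixed center effects at the gated visits. The remaining downside is reliance on a model-based analysis. No new data are collected.
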